14.1 Primary Endpoint: Time to Recovery

14.1.1 Primary Objective: Derivation and Analysis of the Primary Endpoint Time to Recovery

The primary efficacy variable is the time to recovery, defined as the time from first dose (Day 1) through Day 28 to first occurrence of WHO 9-point ordinal scale 3 or less, in days:

- Time to recovery (days) = (Date/time of first ordinal scale for clinical severity <= 3 – Date/time of first dose)

The rules for the different types of censoring/event below will be followed:

| # | Description | Date of Response or Censoring | Outcome |
|---|---|---|----------|
| 1 | Death from Day 1 up to D60/Study completion | D28 | Censored |
| 2 | Failure at any point and time during the study from D1 up to D28, defined as: * ICU admission leading to treatment discontinuation * use of mechanical ventilation * relapse | D28 | Censored |
| 3 | Participant not confirmed to be eligible based on inclusion criterion 6 (PDEV05 code) | Date of first dose of study drug | Censored |
| 4 | No post-baseline clinical status data | Date of first dose of study drug | Censored |
| 5 | Clinical status ≤ 3 before Day 28 | Date of clinical status ≤ 3 | Event |
| 6 | Clinical status > 3 through Day 28 without death or failure | D28 | Censored |
| 7 | Early discontinuation before or on Day 28 without improvement, failure or death | Date/time of last available result of clinical status from Day 1 through Day 28 | Censored |

Number and percentage of participants with and without recovery will be presented.

The hypotheses that will be tested for each dose level using a one-sided stratified log-rank test of distribution of time to recovery with use of corticosteroids at a prednisone equivalent daily dosage of ≤ 15 mg or > 15 mg within 48 hours prior to randomization, and country as stratification factors, are:

- $H_{0i}: HR_i \leq 1$

- $H_i: HR_i > 1$

where

- HR_i denotes the Hazard Ratio of M5049 dose i versus placebo
- i denotes M5049 50 mg BID or M5049 100 mg BID
- $HR_i > 1$ denotes an improvement compared to placebo.

Estimation of the effect of each treatment dose (and 95% two-sided CI) separately compared to placebo will be based on hazard ratio from stratified Cox-model of recovery hazard rate, with terms for treatment group (each active treatment separately against placebo), use of corticosteroids at a prednisone equivalent daily dosage of ≤ 15 mg or > 15 mg within 48 hours prior to randomization, and country. Ties will be handled using the discrete method.

Cumulative distribution function for time to recovery will be estimated via Kaplan-Meier (product limit) method by treatment group and presented together with associated statistics (median time to recovery, recovery rates at Day 7, Day 14, Day 21 and Day 28) including the corresponding two-sided 95% CI. The estimates of the standard error (SE) will be computed using Greenwood's formula.

A large, bold, red watermark consisting of the letters 'C', 'C', and 'I' is centered on a black rectangular background. The letters are stylized and slightly overlapping.

CCI

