Compliance (%) = $100 \times (\text{Number of tablets taken} / \text{Number of planned tablets to be taken})$

where:

- Number of tablets taken = (total number of tablets dispensed – total number of tablets returned)
- Number of planned tablets = Planned duration of exposure (i.e. 14 days) × Number of planned tablets per day (i.e. 8 tablets/day) = 112 tablets

In case of study drug not returned and amount returned missing, it will be assumed that all tablets have been taken for compliance calculation. Considering that 120 tablets are dispensed to ensure the subject has sufficient stock, compliance for subjects not returning any tablet will be $107\% = 120/112 * 100$.

The summary of treatment exposure will include the following information:

- Exposure duration (days)
- Cumulative dose (mg)
- Compliance (%)

A separate listing will be presented for:

- Treatment exposure
- Drug accountability
- Exposure and compliance parameters
- Subjects receiving investigational product(s) from specific kits.

14 Efficacy Analyses

The following analyses will be performed based on the ITT by treatment group except when otherwise stated.

For the time to event analysis, failure will be defined as follows:

| Definition | eCRF page | Value |
|--|--|--|
| Invasive or Non-Invasive Mechanical Ventilation | Ordinal Scale on Clinical Severity | Ordinal Scale on Clinical Severity >= 5 |
| ICU admission leading to treatment discontinuation (both the following conditions) | End of study treatment AND Hospitalization | Did the subject complete the full course of study treatment? = NO AND Date of treatment completion/discontinuation occurring during ICU/HDU stay |
| Relapse | Date of Visit | Reason for Relapse completed |

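### The recovery, SpO2 and discharge tables in the SAP let one participant be both an event and censored at Day 28, with no stated precedence, and the event rows stop a day short of the definition

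*SAP*

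**What the plan says.** The primary variable in SAP 14.1.1 is the "time from first dose (Day 1) through Day 28 to first occurrence of WHO 9-point ordinal scale 3 or less". A numbered table then assigns outcomes:

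- Row 1, "Death from Day 1 up to D60/Study completion": censored at D28.
- Row 2, "Failure at any point and time during the study from D1 up to D28": censored at D28. Failure means ICU admission leading to treatment discontinuation, mechanical ventilation, or relapse.
- Row 3, "Participant not confirmed to be eligible based on inclusion criterion 6 (PDEV05 code"): censored at first dose.
- Row 5, "Clinical status ≤ 3 before Day 28": event on the date of that score.
- Row 6, status above 3 "through Day 28 without death or failure": censored at D28.

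The failure table at the start of SAP 14 codes ventilation as "Ordinal Scale on Clinical Severity >= 5" and relapse as "Reason for Relapse completed" on the visit page. Score 5 on the scale in SAP 14.2.2 includes high-flow oxygen.

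SAP 14.2.3 (SpO2) uses the same rows 1, 2 and 5. SAP 14.2.9 (discharge) has the same rows 1 and 2, with the event in row 3. Protocol 10.4.2, 10.4.3.3 and 10.4.3.9 censor deaths and failures at Day 28 without condition. Only completers and withdrawals are limited to those without the event.

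**The concern.** Two sequences satisfy an event row and a censoring row at once: (i) a first qualifying score, then failure by D28 or death by D60; (ii) failure, then a first qualifying score before Day 28. Two programmers could follow the table faithfully and build different primary datasets.

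If rows 1 and 2 override the event row, a recovery on Day 6 is erased by a death on Day 55. The recovery rates at Days 7, 14, 21 and 28 then depend on later events, some of them after Day 28, and the hazard ratio no longer describes the first-occurrence endpoint. If the event row governs, sequence (i) raises no such problem, but a recovery after failure counts as an event despite row 2.

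The Day 28 boundary is a separate inconsistency. The definition includes Day 28, but the event rows exclude it.

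**Working it through.** **Rule logic.** The plan gives no figure that depends on this, so there is nothing to reproduce. Cross recovered (yes/no) with failed by D28 (yes/no) and death (none, by D28, Day 29–60): 2 × 2 × 3 = 12 combinations. Those with recovery before Day 28 are:

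| Failure by D28 | Death | Rows met in 14.1.1 |
|---|---|---|
| no | none | 5 (event) |
| no | by D28 | 1 (censored) and 5 (event) |
| no | Day 29–60 | 1 and 5 |
| yes | none | 2 and 5 |
| yes | by D28 | 1, 2 and 5 |
| yes | Day 29–60 | 1, 2 and 5 |

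Five of the six recovered combinations receive contradictory outcomes. None of the six unrecovered ones does. Rows 6 and 7 carry their own exclusions, so the table handles exclusivity inside rows, but rows 1, 2 and 5 have none. For ICU admission and ventilation (SAP 14.2.5 to 14.2.7) the SAP takes the earlier of the competing dates. The three favourable-event tables have no such rule.

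**Day 28.** A first score of 3 or less on Day 28 is not row 5, which ends before that day. It is not row 6 either, which needs a status above 3 throughout. In 14.2.9 a discharge on Day 28 falls under row 4 and is censored.

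**Size per case.** Protocol 4.1 plans 150 participants randomized 1:1:1, so 150/3 = 50 per arm. With follow-up complete to Day 28, one recovery counted under one reading and censored under the other moves that arm's rate by 1/50 = 2.0 points at every landmark from its date onwards. Three cases give 6 points.

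**Hazard ratio, illustration.** Assumptions: two identical arms of 50, exponential-type recovery times in whole days, k randomly chosen recoveries in one arm reset to censored at D28, 300 draws, and an unstratified Cox model with discrete ties. The SAP also uses discrete ties, but stratifies by corticosteroid use and country.

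| Recovered by Day 28 | SE of log HR at null | 95% CI at null | HR, k = 1 / 2 / 3 | Shift in SE, k = 1 / 2 / 3 |
|---|---|---|---|---|
| 30 of 50 | 0.261 | 0.60–1.67 | 0.951 / 0.901 / 0.855 | 0.19 / 0.39 / 0.58 |
| 35 of 50 | 0.243 | 0.62–1.61 | 0.951 / 0.905 / 0.861 | 0.20 / 0.40 / 0.60 |
| 40 of 50 | 0.229 | 0.64–1.57 | 0.950 / 0.904 / 0.860 | 0.23 / 0.44 / 0.65 |

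**Overlap in both arms.** A second illustration assumes exponential recovery, a placebo median of 9 days and 2,000 trials. A set share of each arm is marked as overlapping and counts only if recovered. Under override:

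| True HR | Overlap, placebo / active | HR under override |
|---|---|---|
| 1.0 | 4% / 4% or 10% / 10% | 1.00 |
| 1.0 | 10% / 4% | 1.15 |
| 1.0 | 4% / 10% | 0.87 |
| 1.5 | 4% / 4% | 1.42 |
| 1.5 | 10% / 10% | 1.35 |

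Equal overlap leaves a null unchanged but pulls a real effect towards 1.

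**The case against.** The strongest reply is that the text already favours override:

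- The protocol's death and failure sentence is unconditional, while the two sentences after it are conditional.
- Relapse, as defined in Protocol 4.8 and SAP 14.2.12, requires earlier discharge with sustained SpO2. As a failure it does almost nothing unless row 2 overrides.
- The D60 window in row 1 changes little for unrecovered participants, who are mostly censored at D28 anyway. Early discontinuers who later die are the main exception.
- Row 3 has little effect unless it overrides row 5.

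All of this stands as evidence of a leaning. It does not amount to a rule. No sentence says that the rows apply in order, and override contradicts both the first-occurrence definition and row 5.

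A reader might infer the stronger claim that the SAP does erase recoveries and so biases the primary estimate. The documents do not support that, because they never say which row governs. Nor do they give any rate for recovery after high-flow oxygen or ventilation, so sequence (ii) is plausible but of unknown frequency. Entry criteria exclude patients on ventilation or expected to need it within 24 hours, and cap FiO2 at 0.4.

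It is also fair to say that the Day 28 boundary is a one-day wording slip, that SAP 9 treats all tests as exploratory, and that text after the Kaplan-Meier paragraph in 14.1.1 is redacted. Protocol 10.4.2 defers intercurrent-event analyses to the analysis plan, and the SAP's modification history keeps a sensitivity analysis for the primary endpoint. An alternative version may already exist there.

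**Conclusion.** The point holds as a contradiction between stated rules in three tables, including the primary one, together with a separate one-day mismatch. The protocol sections do not resolve either. Whether a later failure or death should cancel a recovery is partly an endpoint decision for the sponsor. What the plan lacks is a statement of that decision.

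The likely effect is small. The number of overlapping participants is unknown and may be zero. Each one moves an arm's rate by about 2 points, assuming 50 per arm. One to three in a single arm shift the hazard ratio by about 0.2 to 0.6 standard errors under the assumed recovery rates, well inside the confidence interval. A reader might infer that the trial's conclusion is at risk, but neither these figures nor the exploratory status supports that.

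Severity is minor to should-fix. Confidence is moderate: the visible tables are clear, but the redacted text could contain a rule or the alternative analysis.

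**What to change.** Before unblinding:

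1. In the event rows of SAP 14.1.1, 14.2.3 and 14.2.9, replace *before* Day 28 with *through* Day 28, and align row 4 of 14.2.9.
2. Make the rows mutually exclusive by stating one precedence for event-then-failure-or-death and one for failure-then-event. To keep the first-occurrence endpoint, an event that precedes any failure or death counts on its date, and rows 1 and 2 apply only to participants with no earlier event. Say explicitly whether an event after a failure is counted or censored. If the sponsor instead intends recovery without later failure or death, redefine the endpoint in those words. In either case report the other version as a named sensitivity analysis, unless the redacted text already has it.
3. In 14.1.1 and 14.2.3 only, state whether row 3 overrides row 5. Section 14.2.9 has no eligibility row.
4. Align Protocol 10.4.2, 10.4.3.3 and 10.4.3.9.

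The cost is wording in three SAP tables and three protocol sections, plus minor programming. No new data are needed. If override was intended, the sponsor must also make an explicit endpoint choice, which is more than an edit. Choosing the rule after unblinding would be a data-dependent decision on the primary endpoint.

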3.2 Part B Objectives

OBJECTIVES	ENDPOINTS (OUTCOME MEASURES)
Primary Efficacy	
To evaluate the time to recovery in participants hospitalized due to COVID-19 pneumonia with M5049 compared to placebo.	Time to recovery from Day 1 through Day 28, defined as time from Day 1 to first occurrence of WHO 9-point ordinal scale 3 or less.
Primary Safety	
To assess the safety of M5049 compared to placebo.	
 • Incidence of TEAEs, AESIs, TEAEs leading to treatment discontinuation, and SAEs from Day 1 through Day 60. • Clinically significant changes in laboratory parameters and ECGs from Day 1 through Day 28.
Secondary	
To assess the proportion of participants free of respiratory support with M5049 compared to placebo.	Alive and not requiring supplemental oxygenation (including any supplemental oxygen, noninvasive or mechanical ventilation and ECMO) through Day 28.
To evaluate the change in clinical status with M5049 compared to placebo.	Clinical status from Day 1 through Day 60 (on a 9-point ordinal scale): 
 9. Uninfected: no clinical or virological evidence of infection. 10. Ambulatory: no limitation of activities. 11. Ambulatory: limitation of activities. 12. Hospitalized, mild disease: hospitalized, no oxygen therapy. 13. Hospitalized, mild disease: oxygen by mask or nasal prongs.

OBJECTIVES	ENDPOINTS (OUTCOME MEASURES)
	14. Hospitalized, severe disease: noninvasive ventilation or high flow-oxygen. 15. Hospitalized, severe disease: intubation and mechanical ventilation. 16. Hospitalized, severe disease: ventilation + additional organ support – e.g., pressors, RRT, ECMO. 17. Death.
To assess normalization of oxygenation status with M5049 compared to placebo in participants who are alive and not on mechanical ventilation.	Time to SpO ₂ of ≥ 94% sustained for at least 24 hours in room air from Day 1 through Day 28.
To evaluate the numbers of deaths with M5049 compared to placebo.	All-cause mortality (Day 1 through Day 60).
To evaluate clinical deterioration with M5049 compared to placebo.	
 • Time to ICU (Day 1 through Day 28). • Time to invasive mechanical ventilation (Day 1 through Day 28). • Time to noninvasive mechanical ventilation (Day 1 through Day 28).
To assess the length of stay in the ICU with M5049 compared to placebo.	Total days in ICU from Day 1 through Day 60.

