14.2.9 Total Days in the Hospital and Time to Hospital Discharge

Total days in the hospital will be based on data collected on the ‘Hospitalization’ eCRF page.

Total days in the hospital are defined as the sum, for all hospitalization events, of the time from first dose to the date of hospital discharge, in days:

- Total days in the hospital (days) =
 First hospitalization: *Date of hospital discharge – Day 1 + 1*
 +
 Subsequent hospitalization: *Date of discharge – date of admission + 1*

In other words, in case of hospital admission prior to and discharge after first dose, date of first dose will be used in place of date of hospital admission for calculation of total days in the hospital. In case of multiple hospitalizations, the total number of days of each event will be added up.

The following information will be presented:

- Number and percentage of participants with more than one hospital admission (only non-consecutive hospitalization will be included in the count)
- Number and percentage of participants in the following discharge categories: death in hospital, discontinuation in hospital, discharged from hospital.
- Summary statistics of duration of hospital stay.

In addition, time to hospital discharge will be based on data collected on the ‘Hospitalization’ eCRF page from Day 1 through Day 28.

The time to hospital discharge, defined as the time from first dose (Day 1) to the date of first hospitalization discharge, in days:

- Time to hospital discharge (days) = (Date of first hospitalization discharge – Date of first dose)

The rules for the different types of censoring/event below will be followed:

| # | Description | Date of Event or Censoring | Outcome |
|---|-------------|----------------------------|---------|
|---|-------------|----------------------------|---------|

| | | | |
|---|---|--|----------|
| 1 | Death from Day 1 up to D60/Study completion | D28 | Censored |
| 2 | Failure at any point and time during the study from D1 up to D28, defined as: * ICU admission leading to treatment discontinuation * use of mechanical ventilation * relapse | D28 | Censored |
| 3 | Hospital discharge before Day 28 | Date of hospital discharge | Event |
| 4 | No hospital discharge before Day 28/discontinuation without death or failure | Earliest between D28 and date of discontinuation | Censored |

Analyses will be performed as specified in Section 14.2.3.

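### SAP event rows for recovery and hospital discharge stop before Day 28, although both endpoints run through Day 28 (minor)

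*SAP*

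**What the plan says.** **Window.** Protocol 3.2 sets the primary endpoint as "Time to recovery from Day 1 through Day 28", and Protocol 10.4.2 uses the same window. The lead sentence of SAP 14.1.1 agrees: the variable is "defined as the time from first dose (Day 1) through Day 28 to first occurrence of WHO 9-point ordinal scale 3 or less". Time to hospital discharge has the same window in Protocol 3.2 and 10.4.3.9, and SAP 14.2.9 takes discharge data from Day 1 through Day 28.

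**Recovery rows, SAP 14.1.1.**
- Row 5 (event): "Clinical status ≤ 3 before Day 28".
- Row 6 (censored at D28): "Clinical status > 3 through Day 28 without death or failure".
- Row 7 (censored at the last available status): "Early discontinuation before or on Day 28 without improvement, failure or death".

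**Discharge rows, SAP 14.2.9.**
- Row 3 (event): "Hospital discharge before Day 28".
- Row 4 (censored at D28 or at discontinuation, whichever is earlier): "No hospital discharge before Day 28/discontinuation without death or failure".

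**SpO2 improvement, SAP 14.2.3.** The event row has the same cut-off before Day 28. The matching censoring row requires SpO2 below 94% in room air through Day 28. The event is dated at the first reading that goes on to be sustained.

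**The concern.** An event table should place every participant in exactly one row and should reproduce the endpoint it implements. These tables do neither for an event that first occurs on Day 28.

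The case can arise. Clinical status is scored daily in hospital and Day 28 is a scheduled visit (Protocol 1.2, SAP 14.2.2), so a first score of 3 or less on that day is observable. The Day 28 recovery and discharge rates, with 95% confidence intervals, are planned outputs.

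For discharge, following the table literally lowers the Day 28 rate. For recovery, two programmers could code the same participant differently. SAP section 7, which lists changes from the protocol's planned analyses, mentions only the stratification factors. The shorter window is therefore not declared as an intended change.

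**Working it through.** No figure in the plan needs to be reproduced here. The check has two parts.

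**1. Applying the rows.** Take a participant with no death, failure, ineligibility or early discontinuation, and vary the day of the first event.

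| First event | Recovery (14.1.1) | Discharge (14.2.9) |
|---|---|---|
| Day 27 | row 5, event | row 3, event |
| Day 28 | no row | row 4, censored at D28 |
| Day 29 | row 6, censored at D28 | row 4, censored at D28 |
| Never | row 6, censored at D28 | row 4, censored at D28 |

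On Day 28, recovery row 5 fails because the event is not before Day 28. Row 6 fails because the score did not stay above 3 through Day 28. Row 7 fails because it needs early discontinuation without improvement. In the discharge table, row 4 applies because there was no discharge before Day 28.

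The wording cannot safely be read as loose shorthand. Row 7 of the recovery table says before or on Day 28, the special-case table in 14.2.1 says on or before Day 28, and the failure, ICU and ventilation rows run up to D28.

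**2. Size, by illustration.** Inputs:
- 150 participants planned, 1:1:1, so about 50 per arm (Protocol 4.1).
- First dose is on Day 1 (SAP 9.4), so Day 28 is about 27 elapsed days.
- Median m of 7 to 16 days. This spans background figures in the protocol's summary of changes: recovery in 7 to 9, 10 and 15 days, and clinical improvement in 16 days. These are not design assumptions.
- Exponential time to recovery, an assumption made here.

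Share first recovering on Day 28 = exp(−26·ln2/m) − exp(−27·ln2/m).

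| m (days) | Day 28 share | Per arm of 50 | Of 150 | Cumulative rate without Day 28 | With Day 28 |
|---|---|---|---|---|---|
| 7 | 0.0762 − 0.0690 = 0.72% | 0.36 | 1.08 | 92.4% | 93.1% |
| 9 | 0.1350 − 0.1250 = 1.00% | 0.50 | 1.50 | 86.5% | 87.5% |
| 10 | 0.1649 − 0.1539 = 1.10% | 0.55 | 1.66 | 83.5% | 84.6% |
| 15 | 0.3008 − 0.2872 = 1.36% | 0.68 | 2.04 | 69.9% | 71.3% |
| 16 | 0.3242 − 0.3105 = 1.37% | 0.69 | 2.06 | 67.6% | 69.0% |

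These counts are upper figures, because participants who die or meet the failure definition are handled by rows 1 and 2 and leave the affected pool. Discharge was not modelled separately. If it followed a similar curve, its loss would be of the same order.

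**The case against.** **No row censors a Day 28 recovery.** The lead sentence of SAP 14.1.1 includes Day 28, and row 6 leaves out anyone who reached 3 or less on that day. The reading that agrees with the protocol is that row 5 is loosely worded and the case is an event. This stands. A reader might infer that the primary endpoint certainly loses its last day of events, but the documents show an unclassified case, not a stated loss. The objection does not help discharge, where row 4 censors explicitly.

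**SpO2 is a different case.** A reader might treat 14.2.3 as the same error. That endpoint needs at least 24 hours of sustained saturation and is dated at onset, and Protocol 9.1.2 records both the start and the end of the 24 hours. An onset on Day 28 would normally be confirmed on Day 29, outside the window, so requiring an onset before Day 28 is arguable. This also stands. What remains is that such an onset fits neither row 5 nor row 6.

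**The cut-off is not a bias.** A reader might note that unfavourable rows include Day 28 while favourable ones do not, and infer a slanted analysis. The inclusive rows cover other participants: those who fail, or who discontinue without improvement. The wording is identical for all arms, and nothing in the documents points to a between-arm bias.

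**D28 may mean elapsed time.** Times are date/time differences for recovery (SAP 9.5 and 14.1.1). If the cut-off were 28 elapsed days, a recovery on study Day 28 would fall inside it. SAP 9.4 favours the study-day reading, but the SAP does not say how D28 is applied. This adds to the ambiguity and does not resolve it.

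**Conclusion.** The inconsistency is real and minor. The discharge rule contradicts its endpoint for a Day 28 discharge. The recovery rule leaves a Day 28 recovery undefined, with the lead sentence pointing to an event. For SpO2, an error in the cut-off is not established; only the wording needs clarification.

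The likely effect is about one percentage point on a Day 28 rate and about 1 to 2 of 150 participants at most. It rests on an assumed exponential curve and on background medians that are not design inputs. The median and hazard ratio would hardly move. The protocol calls the study exploratory and the SAP treats all its tests as exploratory, so the point does not threaten the primary result.

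**What to change.** - In SAP 14.1.1 row 5 and in SAP 14.2.9 rows 3 and 4, change *before Day 28* to *on or before Day 28*. Each first event on Day 28 then falls in one row, as an event.
- In SAP 14.2.3, state whether an onset on Day 28 counts when its 24-hour confirmation falls on Day 29, and word rows 5 and 6 so that every case fits one row.
- In the same edit, say whether D28 means the study day or 28 elapsed days.

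The cost is three wording edits and two clarifying statements in the SAP, with row wording to match in 14.2.3, made before unblinding. Nothing changes in data collection, design or sample size.
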